Eligible participants will continue with rest of the assessment – see Baseline Assessment booklet. We will split this part of the assessment in multiple visits if necessary or if the participant makes the request. The sequence of administering these tests might vary and it can be altered at the discretion of the RA and/or upon the request of the participant. The assessment consists of perceptual questions about participant's social support, social network, physical and emotional well-being, and quality of life. Other questions are related to participant's ability to remember words and understand written sentences, and follow instructions. The assessment is multimodal - paper and pencil, verbal, and interactive using a computer-tablet. Some instructional words will be adapted accordingly when tests are administered on a computer-tablet instead of in paper and pencil. For example, instead of circle/mark the correct answer, it might read select/choose the best answer. The RA will paraphrase the instruction statements accordingly so the participant understands it. For the quality assurance and adherence to protocol, the assessment may be audio recorded. No recording will be done if participant refuses to give consent for the recording. Breaks will be provided as needed.

All eligible participants will receive a tablet with internet connection for the duration of the study.

Training sessions (2 training sessions):

Eligible participants regardless of their randomization condition (Tablet or FSS) will receive 2 training sessions to learn to use the tablet and the FSS system. The first training session will take place in small group format in the office, at a local community center, or over video-conference/telephone and will

Version: 3.1

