last between 60 – 90 minutes. Breaks will be provided accordingly. The second session will be either inperson in small-group or individual format, or will occur over the phone/video-conference. The second session will be approximately 30-60 minutes. These sessions are interactive and involve a lot of practice (training scripts are provided in the MOP). The training scripts are NOT intended to be followed verbatim. These are detailed protocols for the RA to follow. Depending on the skills of the participant, the RA will have to provide more detail or more practice exercises as part of the training. The sequence of the training topics might vary at the discretion of the RA and the participant. More training sessions might be provided upon the participant's request. It depends on the skills and ability of the participant to use the tablet. The training also encompasses information on exercise safety.

Study Intervention

Participants will be randomly assigned to Fittle Senior System (FSS) or a tablet control (TC) condition. The duration of the intervention is 12-week followed by a 12-week maintenance phase. Participants will be assessed at baseline, 3 months post active intervention and 3 months post maintenance phase (6 months following active intervention). Each assessment will last about 2.5 hours. It has paper and pencil questionnaires such as basic socio-demographic information, experience with computer/internet, perceived barriers to exercise, social support and isolation, and general quality of life; and physiological measures such as Timed Up and Go, grip strength, balance, and walking. All participants will be compensated at the rate of \$30/assessment. No research-related activity will begin without a written informed consent from the participant.

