A number of measures are required to address our specific aims. This will allow us to examine the efficacy of the FSS intervention and potential moderators of treatment effects (e.g., gender, age, race/ethnicity) as well as factors that mediate the relationship between treatment and outcome (e.g., social support, self-efficacy). We will examine potential moderating and mediating variables using structural equation modeling techniques guided by current theories of behavior change (e.g., Bandura, 2001; Ajzen, 1991) and technology acceptance and use among older adults (e.g., Venkatesh et al., 2003; Melenhorst et al., 2006; Mitzner et al., 2010). Our study design will also allow us to examine maintenance of treatment effects over time.

Prior to any formal analyses, we will compute descriptive statistics (e.g., frequencies, means, standard deviations) for each variable. Frequency counts will be obtained on interval, ordinal, and categorical data. Variables will be checked for non-normality and, if needed, will be transformed to achieve a normal distribution or hypotheses will be tested using non-parametric tests. Groups-by-periods and differences-against-totals plots will be produced to inspect the data for trends. Multivariate dependencies will be studied using scatter plots and multiple correlation coefficients.

The overall study design is a 2 (treatment condition) x 3 (three measurement points), between-within group design with one between subjects factors and one within subjects factor. There will be three measurement points (baseline, 3 months and 6 months). For the main analyses we will use the General Mixed Model. This model is suitable for analysis of unbalanced data, does not require the assumption of

Version: 3.1

normality of the dependent variable (in fact it can be used when the response of interest is a binary variable or a count variable), can incorporate account for missing data in statistical models and is implemented in different analytical software packages such as the Proc MIXED in SAS.

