In addition to the longitudinal analysis, the model also permits cross-group analyses, which we will perform at baseline, 3 and 6 months post intervention follow-ups. Baseline variables that are statistically significant at baseline will be modeled as covariates. Given our comprehensive outcome measures, where appropriate, we will create composite outcome measures for constructs such as social support/social isolation, and self-efficacy employing multivariate solutions such as principal component analyses and similar multivariate approaches for data reduction.

Data containing missing points due to attrition will be included in analyses and data will be analyzed using the intention-to-treat approach. Multiple imputation techniques will be used to impute missing follow-up outcome values and compared to the data for completers only. We realize that there will be mediators (self-efficacy) as well as moderators (e.g. gender) on particular analyses, which will be managed through structural equation modeling approaches guided by theories of behavior change and technology acceptance. Post-hoc tests of means for any statistically significant main effect will be accomplished using the paired t-tests procedure. Given that there are multiple dependent measures, there is an increased possibility of spurious Type 1 family-wise alpha error. Corrections such as the Bonferroni are very conservative and a substantial loss of power is evidenced when more than five contrasts are subjected to adjustment using this approach. As a result, to minimize the possibility of Type 1 errors but to reduce the likelihood of a Type II error, the test-wise alpha for each F contrast will be set at p < .01.

In addition, as noted, use of FSS will be tracked over time. Specifically we will gather information regarding process measures such as frequency of use, features used, social interactions, changes in use and patterns of use over time. This data will be summarized and described using descriptive statistics such as frequencies and means. We will also compute a composite dosage measure. This will also allow us to conduct a dose response relationship for those in the FSS group to examine if level of exposure to FSS is significantly associated with pretest-posttest change on the outcome measures. Finally, we will examine the intervention evaluation data for both groups and the usability measure for those assigned to the FSS condition.

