After IRB approval, the research team will contact potential recruitment sites and inform them about the study. These sites will be provided with IRB approved promotional materials (flyer) for recruitment. At the same time, the UM and WCM PR departments will be informed and notified of the ongoing research. The PR departments will be provided with the promotional materials for the study. UM and WCM sites such as those that make regular postings and newsletters will also be contacted and provided with an approved ad or communication regarding the project. The CITI certified staff member within the project plans to also attend health fairs and /or senior centers and events and have flyers available at various community centers so that potential participants can learn of the study. The IRB approved ad/flyer will also be posted in non-institutional newsletters and advertisement sections.

Version: 3.1

Promotional material use in this study are: flyer and advertisement blurb.

Once potential participants learn of the study, they will phone the recruitment phone line. A brief telephone interview will be conducted. If these participants are eligible for the study, they will then be scheduled for the baseline assessment.

Participants will not have any financial liabilities for participating in the study. The study provides financial compensation for their time/effort in completing the assessment. Participants will also receive roundtrip MetroCards for visits to the office/community center for the WCM site.

15) Local Number of Subjects

We anticipate to screen a maximum of 600 participants in Phase 2. We expect 181 participants to complete the study. The participants will be from Weill Cornell Medicine and University of Miami.

16) Confidentiality

This study does not collect specimens. The data are questionnaire based and participants will be completing them on paper or online using a secure and unique log. All the data will be stored and secured using the procedure implemented by the Center for Cognitive Neuroscience and Aging. The access to records and participants data will be allowed only to the study personnel. The data will not contain any identifying information.

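### Site is not pre-specified in the analysis of this two-site trial, and no site stratification is stated: a modest, cheaply repaired loss of precision

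*Combined protocol and SAP*

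**What the plan says.** All references are to the combined protocol and SAP.

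- **Sites.** Section 15 (Local Number of Subjects): "The participants will be from Weill Cornell Medicine and University of Miami". Section 11 (Setting) names the same two centres. The split between them is not given.
- **Size.** Section 15: "We expect 181 participants to complete the study".
- **Allocation.** Section 5, Study Intervention: "Participants will be randomly assigned to Fittle Senior System (FSS) or a tablet control (TC) condition". Neither this nor the similar sentence earlier in section 5 mentions a ratio, blocks, strata or site.
- **Delivery.** Section 5, Training sessions: "The first training session will take place in small group format in the office, at a local community center, or over video-conference/telephone". The same section adds: "The training scripts are NOT intended to be followed verbatim". Detail, practice and order may vary with the participant's skills and at the research assistant's discretion.
- **Model.** Section 7, Phase 2, sets out a 2 x 3 design, described as a "between-within group design with one between subjects factors and one within subjects factor". The between-subjects factor is treatment; the within-subjects factor is time (baseline, 3 and 6 months). Cross-group comparisons at each time point are planned alongside the longitudinal analysis.
- **Covariates.** Section 7: "Baseline variables that are statistically significant at baseline will be modeled as covariates". Site is not named here, nor among the example moderators (gender, age, race/ethnicity).

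**The concern.** Site is known before randomisation, and in a two-site behavioural trial it may well predict outcome: the participants, recruitment sources, venues and staff can all differ. The usual course is to decide in advance how site is handled in both allocation and model. This plan does neither explicitly.

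The covariate rule does not fill the gap. Under proper randomisation, a baseline test flags site only about as often as the test's own significance level, so most chance imbalances would stay unadjusted. If allocation were blocked by site, the imbalance would be close to zero and the rule would almost never bring site in, although that is when the model should reflect the blocking.

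At stake are avoidable noise in the treatment comparison, chance error in whichever allocation occurs, or a standard error that does not match the design.

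**Working it through.** **Inputs from the plan.** N = 181 expected completers (section 15); two sites (sections 11 and 15); three measurement points and a test-wise alpha of .01 (section 7).

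**Assumptions, because the plan gives no figures.** 1:1 allocation; site share p = 0.5; between-site difference d of 0.3, 0.5 or 0.8 within-site SDs; a true effect of 0.5 SD for the power figures.

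**Step 1: the plan's own figure.** The 181 cannot be reproduced, since no effect size, SD, power or dropout rate is given. As context, the standard error of a two-arm difference is sqrt(4/181) = 0.149 SD. The difference detectable with 80% power at two-sided .01 is (2.576 + 0.842) x 0.149 = 0.51 SD.

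**Step 2: chance imbalance in site under unstratified allocation.** The SD of the between-arm difference in site share is sqrt(p(1-p) x 4/N) = sqrt(0.25 x 4/181) = 0.074, so the 95% range is +/-14.6 percentage points. An imbalance above 10 points has probability P(|Z| > 0.10/0.0743) = 0.18. A baseline test at .05 would flag site only beyond about 14.6 points, and at .01 only beyond about 2.576 x 7.43 = 19.1 points.

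**Step 3: single-time comparison without baseline adjustment.** Omitting site multiplies the variance by 1 + p(1-p)d² = 1 + 0.25d².

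| d (SD) | Variance factor | SE increase | Effective N | Chance-error SD (0.0743 x d) | Power without site |
|---|---|---|---|---|---|
| 0.3 | 1.0225 | 1.1% | 177 | 0.022 | 77.3% |
| 0.5 | 1.0625 | 3.1% | 170 | 0.037 | 75.4% |
| 0.8 | 1.16 | 7.7% | 156 | 0.059 | 70.8% |

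Power with a site term is 78.5%. The chance-error and SE columns show one effect in two ways: at d = 0.5, sqrt(0.149² + 0.037²) is about 0.153, which is the 3% increase. At a 70:30 site split the SE increases are slightly smaller: 0.9%, 2.6% and 6.5%.

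**Step 4: false-positive rate.** In 20,000 simulated trials per setting at alpha .01, the analysis without site rejected a true null at rates of 0.0100 to 0.0112 under unstratified allocation. There is no meaningful inflation.

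**Step 5: allocation blocked by site, site left out of the model.** At d = 0.5, the simulated SD of the estimate was 0.148 under blocking without a site term, 0.149 under simple randomisation with one, and 0.154 under simple randomisation without one. Blocking therefore already protects the estimate. The reported standard error remains too large, and the test is conservative: simulated type I error was 0.0097, 0.0083 and 0.0053 at d = 0.3, 0.5 and 0.8.

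**Step 6: the group-by-time contrast.** If site adds a constant to a participant's score at every time point, that constant drops out of each change from baseline and so out of the between-arm difference in change. In a check on simulated complete data, adding only a site main effect left the group-by-time estimate at 0.33370 and its standard error at 0.13373, the same with and without site. A site difference in change over time does not drop out; only a site-by-time term takes it up.

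**The case against.** The strongest reply is that the main analysis is the 2 x 3 mixed model with baseline as one of its three measurement points. The plausible site differences (population, surroundings, recruitment source) are mostly stable, exist at baseline and cancel from the group-by-time contrast. This stands. A reader might infer from step 3 that the trial's main analysis forfeits 6% of its information at d = 0.5 (0.0625/1.0625) or 14% at d = 0.8 (0.16/1.16). The documents do not support that: those losses belong to single-time comparisons without baseline adjustment, which section 7 adds to the longitudinal analysis. It also follows that a site main effect alone would do nothing for the main contrast.

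A reader might also infer that allocation ignored site. The plan does not say so. It describes no randomisation method, and silence is not evidence of unstratified allocation. Nor does the latitude in training establish a site effect: section 5 ties it largely to the participant's skills, and nothing shows that it differs between New York and Miami.

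Finally, even in the comparison most exposed to the problem, power falls by only 1.2 points at d = 0.3 and 3.1 at d = 0.5. That limits the size of the point. It does not justify leaving the handling of site to a baseline significance test when a pre-specified term costs almost nothing.

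**Conclusion.** The point holds as a modest one. In a two-site trial, no site stratification is stated, and site reaches the model only through a baseline significance test. The consequence is some loss of precision and chance error conditional on the allocation obtained. A stronger reading, that the treatment effect is systematically biased or the false-positive rate inflated, is not supported.

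For the 3- and 6-month cross-group comparisons without baseline adjustment, the standard error rises by about 1%, 3% and 8% at assumed site differences of 0.3, 0.5 and 0.8 SD. The gain from adjustment shrinks where the baseline outcome already captures the site difference. In the group-by-time contrast, only site differences in change matter, and the plan gives nothing from which to size them. If allocation is blocked by site, it would be wrong to say that the estimate is less precise; the fault is then an overstated standard error.

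The figures rest on the assumed 1:1 ratio, 50:50 site split and site differences. The cancellation result was checked on complete data only.

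**What to change.** In section 7, Phase 2:

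- Pre-specify site and site-by-time as fixed effects in the mixed model, whatever the baseline tests show.
- Include site as a fixed effect in each cross-group comparison on the same footing.
- Present the FSS-TC effect by site descriptively, so that readers can see whether two centres with flexible delivery agree.

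In section 5, Study Intervention, state whether allocation is stratified by site.

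The cost in the mixed model is about three degrees of freedom: one for site plus (3 - 1) x 1 = 2 for site-by-time. Each cross-group comparison loses one. No participants, visits or procedures are added, and the model change can be made even if enrolment is complete.

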When participant is determined as eligible to participate through pre-screening, the RA will schedule a visit with the participant. This first visit could be as long as 2.5 hours depending on the participant. At the start of the visit, the RA is to begin by introducing the ICF to the participant. The RA will read and review the ICF with the participant and make sure he/she understands it before signing the form. The ICF will include permission for audio/video recording for research or education/training purpose. None of the study-related activities can begin until the participant signs the ICF. The RA will provide a signed and dated ICF to the participant for his/her records. In cases where visits do not take place in-person, an electronic consent will be obtained in a REDCap database. If the participant does not have access to a device with an internet connection, the consent form may be mailed to participants for completion and return. No additional study related activities can begin until the consent is fully signed and complete.

The first study-related activity is to further determine whether the participant is eligible for the study. The RA will administer the vision test, the reading comprehension test (i.e., Woodcock Johnson), and the brief memory test (i.e., MMSE). If the visit is conducted over the phone or video conference, the participant will be asked to read a paragraph of the consent form to ensure adequate vision and reading comprehension required for the study. The MSME will not be given remotely, and instead the TICS collected at pre-screening will be used in lieu of the MMSE for these participants. For in-person assessments, the physical test (i.e., TUG) will be given to help assess physical functioning. The TUG will not be required for screening, and ability to complete study exercises will be assessed at phone screening. There is no particular order to administer these tests. If the participant is not eligible to participate because of any of the above-mentioned tests, the RA will administer a brief demographic questionnaire so we can capture the demographics of those who are not eligible for the study. These non-eligible participants will receive \$20 for their time and effort.

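### Baseline significance tests choose the covariates for the month-3 and month-6 group comparisons, so an outcome's own baseline is rarely or never adjusted for; fix that adjustment in advance

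*Combined protocol and SAP*

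**What the plan says.** The statistical plan is in section 7, Data Management, under Phase 2. The main analysis is a mixed model for a design with two arms and three measurement points (baseline, 3 months, 6 months), so baseline is one of the repeated responses. Group comparisons at single visits come on top of that: "the model also permits cross-group analyses, which we will perform at baseline, 3 and 6 months post intervention follow-ups". The next sentence is the only covariate rule in the documents: "Baseline variables that are statistically significant at baseline will be modeled as covariates". No test or threshold is given for that screen. Nothing says that an outcome's baseline value is always adjusted for, and no covariate list is fixed in advance.

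Three other statements in section 7 bear on the point. For the outcome contrasts, "the test-wise alpha for each F contrast will be set at p < .01". The plan commits that "data will be analyzed using the intention-to-treat approach". On missing data, "Multiple imputation techniques will be used to impute missing follow-up outcome values"; imputation of missing baseline values is not mentioned.

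**The concern.** Participants are randomised, so a significant difference between arms at baseline arises by chance. The test does not show whether the variable predicts the outcome, and prediction is what makes a covariate useful. The best predictor of an outcome at month 3 or month 6 will often be its own baseline value, and this rule leaves it out unless the arms happen to differ on it.

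Two things are at stake in these comparisons. One is precision, at a strict alpha of .01 that the plan chose while also wanting to limit Type II error. The other is conditional bias: a baseline imbalance just short of the threshold stays in the estimate uncorrected. The form of the model also depends on the data.

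**Working it through.** **Inputs.** From the documents: 181 expected completers (section 5, Procedures Involved, Phase 2), alpha .01 per contrast (section 7), two randomised arms. Assumed, because the documents give no figure: 1:1 allocation (91 v 90), a true effect of 0.4 SD with 0.3 and 0.5 SD as alternatives, correlation between baseline and follow-up r = .3, .5 or .7, and a screen that is a two-sided between-group test at .05 or .01. The plan has no power calculation to reproduce.

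**1. How often the baseline enters.** Under randomisation the baseline p-value is uniform, so an outcome's baseline passes the screen in 5% or 1% of trials. Simulation gave 4.9% to 5.1% and 1.0%. If the rule covers background characteristics only, the figure is zero.

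**2. Whether the mixed model already adjusts.** With complete data and free arm means at each visit, generalised least squares for the 2 x 3 model gives a month-3 group contrast with variance 1/91 + 1/90 = 0.0221 (outcome SD 1). That is the variance of the raw difference in means. Constraining the baseline means to be equal divides it by 1/(1 - r²) = 1.10, 1.33 or 1.96.

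**3. Power at two-sided .01.** The noncentral t distribution with noncentrality d / (s x √0.0221) was used, where s = 1 unadjusted and s = √(1 - r²) adjusted.

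| True effect | Unadjusted | Always adjusted, r = .3 / .5 / .7 |
|---|---|---|
| 0.3 SD | 28% | 32% / 39% / 59% |
| 0.4 SD | 54% | 58–59% / 69% / 88% |
| 0.5 SD | 78% | 82% / 90% / 98% |

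Simulating the rule itself at 0.4 SD (analysis of covariance if the baseline test is significant, otherwise a t-test) gave about 53%, 54% and 56% with the .05 screen, and 53% to 54% with the .01 screen. The rule recovers almost none of the gain.

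**4. Variance relative to always adjusting.** For a screen at level a with critical value L, the ratio is 1 + (1 - a) r² v / (1 - r²). Here v = 1 - 2Lφ(L)/(1 - a) is the variance of the standardised baseline difference when it is not significant.
- Screen at .05: v = 1 - 2(1.96)(0.0584)/0.95 = 0.759. At r = .5 the ratio is 1 + 0.95 x 0.25 x 0.759/0.75 = 1.24. For r = .3 and .7 it is 1.07 and 1.69.
- Screen at .01: v = 0.925, and the ratios are 1.09, 1.30 (1.31 without rounding to simulation) and 1.88.

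**5. False positives.** Given a standardised baseline difference z, the standardised follow-up difference under no effect is N(rz, 1 - r²). Integrating over z gives:
- Overall, at nominal 1%: 0.9%, 0.8% and 0.5% with the .05 screen; 1.0%, 0.9% and 0.8% with the .01 screen. There is no inflation.
- When the imbalance just misses a .05 screen (|z| from 1.5 to 1.96, about 8% of trials): about 1.6%, 2.3% and 2.7%.
- When |z| is below 1.5 (about 87% of trials): 0.9%, 0.6% and 0.3%.

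An imbalance at the .05 threshold is 1.96 x √0.0221 = 0.29 SD. Left unadjusted, it shifts the estimate by r x 0.29 = 0.09, 0.15 or 0.20 SD.

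**6. Missing baselines.** Rates of 10% and 30%, missing completely at random, are assumed, with follow-up available for all 181. Power at 0.4 SD for r = .3 / .5 / .7:

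| Handling | 10% missing | 30% missing |
|---|---|---|
| Adjust, drop those without baseline | 52% / 63% / 83% | 40% / 49% / 70% |
| Adjust, retain them (equal-baseline model) | 58% / 68% / 86% | 57% / 65% / 81% |

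At 30% missing, dropping them is worse than not adjusting (54%) for r = .3 and .5.

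**The case against.** The strongest reply is that the reach is limited. The main analysis is the longitudinal model, whose group-by-time contrast already subtracts baseline, and the visit-specific comparisons are described as additional. This stands, and the criticism is confined to those comparisons. It also tempers the largest figure. The change contrast has variance 2(1 - r) relative to the raw comparison, so at r = .7 it already has about 81% power for 0.4 SD, and adjustment adds about 7 points to that. At r = .5 the change contrast has variance 1.00 and 54% power, so it offers no advantage there. The plan does not name it as the primary test or as a replacement for the visit comparisons.

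Second, the wording does not say that the screen is a between-group test. That is the natural reading, but it is an assumption.

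Third, the near-miss false-positive rates describe a selected 8% of trials; in most trials the rate is below nominal. That is correct. The point is conditional bias, not overall error.

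Fourth, the missing-baseline figures measure a hazard of the remedy and not a defect in the plan. That is also fair. They are given because a careless fix could do harm.

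**Conclusion.** The concern holds for the month-3 and month-6 group comparisons. On the between-group reading, the rule leaves them unadjusted for the outcome's own baseline in 95% to 99% of trials, or always. Estimates are 1.07 to 1.88 times as variable as they need be over r = .3 to .7. For a 0.4 SD effect, the power forgone is about 5 points at r = .3, 15 at r = .5 and more than 30 at r = .7. These sizes rest on the assumed effect, correlation and 1:1 allocation; the defect in the rule does not. Overall Type I error is not inflated, and the main group-by-time contrast is not at fault. Constraining baseline means to be equal in that main model would be an optional efficiency gain. This is a modest point about prespecification that should be acted on because the remedy is cheap.

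**What to change.** Replace the covariate sentence in section 7 with wording such as:

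> For each outcome measured at baseline, the month-3 and month-6 between-group comparisons adjust for that outcome's baseline value, fixed in advance. Participants with a missing baseline value are retained, by fitting the mixed model with baseline as a response and baseline means constrained equal across arms, or by imputing the baseline value. Outcomes measured only at follow-up are compared without baseline adjustment. Baseline comparisons are descriptive and do not select covariates.

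If background characteristics are also wanted as covariates, list them in advance in the same place.

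The retention rule matters. Section 5 lists among the assessments "physiological measures such as Timed Up and Go, grip strength, balance, and walking", but under the baseline visit it says "For in-person assessments, the physical test (i.e., TUG) will be given to help assess physical functioning", so remote baseline visits may lack that measure. The plan's imputation covers follow-up values only. Dropping these participants would also sit badly with the intention-to-treat commitment.

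The cost is a change of wording and a little more analysis work for missing baselines. No new data are collected.

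### A baseline covariate entered with a single slope cancels from the arm-by-time contrast of the 2 x 3 mixed model, so the stated adjustment may never reach the longitudinal effect

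*Combined protocol and SAP*

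**What the plan says.** All of the analysis text is in the combined protocol and SAP, section 7 (Data Management, Phase 2).

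- The design is a "2 (treatment condition) x 3 (three measurement points), between-within group design", and baseline is a level of the time factor: "There will be three measurement points (baseline, 3 months and 6 months".
- The model is named but its terms are not written out: "For the main analyses we will use the General Mixed Model".
- Arm comparisons at single visits come from the same model: "the model also permits cross-group analyses, which we will perform at baseline, 3 and 6 months post intervention follow-ups".
- The next sentence is the covariate rule: "Baseline variables that are statistically significant at baseline will be modeled as covariates". It gives no significance threshold and neither states nor excludes covariate-by-time terms.
- For missing outcomes: "Multiple imputation techniques will be used to impute missing follow-up outcome values and compared to the data for completers only".

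No treatment contrast is named. The post-hoc rule speaks of main effects and does not mention the arm-by-time interaction. The section describes no other handling of baseline imbalance, such as stratified randomisation, a constrained baseline mean, or analysis of covariance on the baseline value.

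**The concern.** When baseline is itself a response row, a treatment effect that starts after randomisation appears as an arm-by-time difference. The arm main effect averages in the pre-treatment visit and so dilutes the effect. A baseline covariate takes the same value on all three of a person's rows. With one slope it shifts all three fitted means of an arm by the same amount, and that shift vanishes from any difference between visits.

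An analyst who follows the covariate sentence in its usual form could therefore describe the longitudinal effect as adjusted although its estimate and standard error are those of the unadjusted model. Any imbalance in a variable that predicts change would stay in the estimate. The visit-specific comparisons would be adjusted, so the two sets of results could differ for a purely technical reason.

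**Working it through.** **Inputs.** From the documents: two arms, three occasions including baseline, and 181 expected completers (sections 5 and 15). The documents give no effect size, SD, correlation or dropout rate, so there is no planned figure to reproduce. Assumed here: a 91/90 split, outcome SD 1, correlation 0.6 between visits, and the imbalances and slopes stated below.

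**Step 1: algebra.** Let y(i,t) = mu(arm,t) + beta·x(i) + error, with complete data and a common covariance matrix. Generalised least squares gives

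mu-hat(arm,t) = ybar(arm,t) − beta-hat·xbar(arm).

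The last term does not depend on t. For any contrast over time whose weights sum to zero, beta-hat·(xbar1 − xbar0) drops out. The same holds in each imputed data set, and so in the pooled result.

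**Step 2: numerical check, complete data.** In one simulated data set the arm-by-time estimates were −0.002713 (month 3) and 0.227179 (month 6), both without the covariate and with it as a main effect. This held under compound-symmetry and unstructured covariance, and the standard error was unchanged (0.14093 unstructured). In a second data set the month-3 estimate was 0.413464 (SE 0.15512) with no covariate, with a main-effect covariate, and with the outcome's own baseline as covariate.

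**Step 3: when it matters.** Mean arm-by-time estimates at months 3 / 6, with a true effect of 0.30 at both visits and a covariate imbalance of 0.4 SD:

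| Setting | No covariate | Main effect | Covariate-by-visit |
|---|---|---|---|
| Slope constant at 0.4, complete data | 0.298 / 0.292 | 0.298 / 0.292 | 0.296 / 0.291 |
| Slopes 0.5, 0.2, 0, complete data | 0.196 / 0.095 | 0.196 / 0.095 | 0.311 / 0.291 |
| Slopes 0.5, 0.2, 0, about 30% dropout, likelihood | 0.217 / 0.099 | 0.241 / 0.126 | 0.325 / 0.269 |

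The complete-data rows use 200 simulated data sets and the dropout row 60. With dropout related to covariate and arm, adding the main effect moved the estimates by 0.02 to 0.03 SD on average. Most of the bias remained.

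**Step 4: size.** Spurious difference = imbalance × slope of change on the covariate.

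- Imbalance that a test would flag: SE of a baseline difference = sqrt(1/91 + 1/90) = 0.149 SD. The threshold is 1.96 × 0.149 = 0.29 SD at p < .05, or 2.576 × 0.149 = 0.38 SD at p < .01.
- SE of the change contrast: sqrt(2(1 − 0.6)(1/90 + 1/91)) = 0.133.
- Illustration: 0.4 × 0.3 = 0.12 SD, and 0.12/0.133 = 0.9 SE. At the planned test-wise alpha of .01, the conditional false-positive risk for that one contrast is P(Z > 2.576 − 0.90), about 4.7%.
- Range: slope 0 gives 0. An imbalance of 0.29 with slope 0.3 gives 0.087 SD (0.7 SE). An imbalance of 0.4 with slope 0.5 gives 0.20 SD (1.5 SE).
- Outcome's own baseline, equal variances: the slope of change on baseline is rho − 1. A 0.4 SD imbalance then gives 0.4 × (0.6 − 1) = −0.16 SD, or −0.08 to −0.24 SD for rho from 0.8 to 0.4.

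**Step 5: what the fix does to precision.** Per-person variance is 2(1 − rho) for change and 1 − rho² for follow-up adjusted for baseline. The SE ratio is sqrt((1 + rho)/2), which is 0.95 at rho = 0.8 and 0.84 at rho = 0.4, a reduction of about 5% to 16%. A by-visit covariate imbalanced by 0.4 SD inflates the SE by about sqrt(1 + 0.4²/4) = 1.02, so 0.133 becomes about 0.136. A simulated run gave 0.137.

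**The case against.** A reader might infer that the plan has been shown to leave its treatment effect unadjusted, or that its covariate rule is empty. The documents do not support either reading.

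- The plan does not say main effect only, and it does not name arm-by-time as its treatment estimate. Cancellation follows from the usual meaning of the sentence, which is not the only possible one.
- The covariate sentence directly follows the one on visit-specific comparisons and may be meant for those. There the covariate does act: with a constant slope, the simulated month-3 difference moved from 0.459 to 0.299 (truth 0.30).
- A change contrast already removes any imbalance whose effect is constant over time, as the first row of the table shows.
- The plan never says that the outcome's own baseline will be placed on both sides of the model.
- Cancellation is not exact for incomplete data analysed by likelihood, or for other response types, which the plan allows ("it can be used when the response of interest is a binary variable or a count variable"). The shifts found were small: in one binary example the estimate moved from 1.184 to 1.189.
- Over all randomisations the unadjusted contrast is unbiased. A 0.4 SD imbalance is about 2.7 SE and would be expected for a given variable in about 0.7% of randomisations, though more often across many variables.

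All of this stands, and it limits the point without removing it. The rule operates only when an imbalance has been flagged, and in its ordinary form it then does nothing, or almost nothing, to the change contrast. Choosing covariates by a baseline significance test is a separate weakness; pre-specified covariates entered with one slope would cancel in the same way.

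**Conclusion.** The point holds conditionally. If baseline covariates enter the linear mixed model as single-slope main effects, they drop out of the arm-by-time contrast: exactly with complete or imputed data, approximately otherwise. That result depends on no assumed number.

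The size of the harm does. It needs a chance imbalance in a variable that predicts change, or in the outcome's own baseline through regression to the mean. The illustrative 0.12 SD (0.9 SE) rests on an assumed 0.4 SD imbalance and 0.3 slope; the settings tried ran from nothing to about 0.24 SD in absolute size. The documents do not show that the trial's result will be biased, only that the adjustment as worded would not reach the longitudinal contrast.

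**What to change.** In section 7 (Phase 2), name the treatment contrast as the FSS-TC difference at months 3 and 6, and replace the covariate sentence with one of these:

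1. Keep baseline as a response and enter each baseline covariate with its covariate-by-visit term. The outcome's own baseline should not be among these covariates, because it is already a response.
2. Model months 3 and 6 as the responses, with the outcome's baseline value and the other baseline covariates entered by visit. This handles regression to the mean and gives the SE reduction of about 5% to 16% shown above.

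The covariates should preferably be listed in advance.

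The cost is one sentence and a few degrees of freedom: under option 1, three slopes per continuous covariate in place of one. The SE is slightly larger when a by-visit covariate is imbalanced (about 0.133 to 0.137 in the example). Under option 2, people with no follow-up outcome contribute only through the multiple imputation that the plan already includes.
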